## 2. STUDY SUMMARY

Title	A phase II randomized, double-blind placebo-controlled trial to determine if fecal microbiota transplantation is efficacious for hospitalized patients with C. difficile infection history during antibiotic treatment
Short Title and Precis	The GRAFT study
Protocol Number	2017-0789
ClinicalTrials.gov number	NCT03621657
Funding Sponsor	Agency for Healthcare Research and Quality (AHRQ) [name] [contact]
Study Product	OpenBiome fecal microbiota preparation capsule [FMT Capsule DE]
Phase	Phase II study
Methodology	Randomized, double-blind, placebo-controlled trial
Study Duration	1 year
Study Center(s)	Single-center, University of Wisconsin Hospitals and Clinics
Objectives	The primary objective of this study is to compare the gut microbiota and clinical outcomes of oral FMT during antibiotic treatment, immediately following antibiotic treatment, and placebo. The second objective is to assess the safety and feasibility of daily oral Fecal Microbiome Transplant (FMT) as a treatment option.
Number of Subjects	30 (1:1:1 randomization), 10 subjects per group
Diagnosis	Changes in the gut microbiota and C. difficile infection (CDI)
Main Inclusion Criteria	Receiving antibiotics for reasons other than CDI following a recent CDI episode (within last 90 days)
Main Exclusion Criteria	Bowel obstruction or gut motility issues, severely immunocompromised, or admitted to the ICU.
Study Product, Dose, Route, Regimen	FMT will be delivered through oral capsules prepared by OpenBiome. It will be administered in one of two ways depending on the arm of the trial. 1) A low dose of 5 capsules per day during antibiotic treatment and for seven days following conclusion of antibiotics. 2) A single dose of 30 capsules (22.5g) of oral FMT will be given 48-72 hours after antibiotic treatment conclusion.
FDA status of product	Encapsulated fecal microbiota preparation (FMT Capsule DE). Please refer to Finch Therapeutics BBMF # 17194.
	Sourced from human-derived microbes. Please refer to OpenBiome BBMF # 15543, Section F.
	IND: 18262

**Duration of administration** Group 1: 5 capsules of oral FMT per day undergoing antibiotic treatment and for 7 days following conclusion of antibiotic treatment.

Group 2: 30 capsules taken 48-72 hours following conclusion of antibiotic treatment

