**Reference therapy** Placebo: 5 capsules of oral placebo per day undergoing antibiotic treatment and for 7 days following conclusion of antibiotic treatment.

**Statistical Methodology** All data will be analyzed using SAS and R. Patient characteristics will be summarized using descriptive statistics. To assess changes in the gut microbiota, ANCOVA and linear mixed models will be used for longitudinal measurements. Safety and adverse events will be summarized using descriptive statistics.

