### **7. STUDY DESIGN AND ENDPOINTS**

#### **7.1. General Design**

This is a phase II, double-blind, randomized, placebo controlled trial assessing the effects of either daily (group 1) or one-time (group 2) oral FMT on the composition and function of the gut microbiome compared to placebo (group 3) in a population of patients with a history of CDI currently on antibiotics for a reason other than current CDI. Participants will be 18 years of age or older, have 72 hours or less of an antibiotic and meet all inclusion criteria while having no exclusion criteria prior to randomization. Patients will be randomized at a 1:1:1 ratio using permuted blocks (block size=10). Randomization will be double-blinded. Each subject (n=30) will be followed for 6 months. Stool samples will be taken at baseline and every 3 days  $\pm$  1 day from all subjects regardless of treatment group while the patient is hospitalized. If/when a patient is discharged from the hospital, the patient will continue to provide stool samples every three days during FMT. Following completion of the FMT intervention, the patient will provide stool samples once weekly for the 1 month follow-up period. All patients will be asked to complete a patient diary to report diarrhea history.

Up to one gram of stool will be sent to Finch therapeutics for additional 16s rRNA sequencing.

**Intervention:** There are 2 intervention groups for this study. Both groups will receive oral FMT capsules from OpenBiome for the prevention of CDI during antibiotic treatment. All patients will fast (clear liquids only) for a minimum of 2 hours prior to administration and 1-hour post-administration for the daily groups and be fasting for 8 hours prior and 1 hour post FMT consumption for the single dose group. The capsules will be administered in the patient's room while admitted or in the ID clinic or CRU if the patient is an outpatient and the first dose will occur under direct observation. Patients admitted to the hospital as well as all patients in the single dose group will be observed for 30 minutes post-administration to ensure the capsules are safely consumed. Hospitalized patients need to be observed 30-minutes post-administration following only the first dose. As mentioned above, the oral FMT capsules will be administered in two ways:

**Group 1:** This group will receive daily oral FMT capsules. Five capsules will be administered each day of the

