patient's antibiotic treatment plus seven days post-antibiotic treatment.

**Group 2:** This group will receive 30 oral FMT capsules one time 48-72 hours following completion of antibiotic treatment.

**Oral FMT capsules:** Capsules contain fecal microbiota sourced from healthy donors and screened for pathogens.

**Control:** The control is an oral placebo capsule identical to the FMT capsules given to the intervention groups and will be provided by OpenBiome. The placebo capsule consists of glycerol and saline and will be administered daily as five capsules per day during the duration of antibiotic treatment plus an additional seven days post-antibiotic treatment (group 3). Patients will be fasting (clear liquids allowed) for at least 2 hours prior to administration and at a minimum of 1-hr post-administration (Appendix 17.1)

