## **9. STUDY AGENT**

### **9.1. Description and Formulation**

DE is encapsulated fecal microbiota sourced from human-derived microbes. The human source generating the fecal microbes has been extensively screened for infectious pathogens and microbiome mediated diseases using a standardized process (found in OpenBiome's BBMF # 15543, Section F). Additionally, the capsule delivery vehicle enables *targeted deposition* of the investigational active pharmaceutical ingredient into the colon.

**DE capsules:** The OpenBiome FMT Capsule DE contains frozen human fecal microbiota filtered to 330 microns, theobroma oil, glycerol, hide bovine gelatin, sodium lauryl sulfate, colorants FD&C, and titanium dioxide. The material is contained in a two capsule system: an interior gelatin capsule that houses the drug substance, and an exterior acid-resistant capsule for delivery of the drug substance past the stomach. The product should be stored at -20°C to -80°C. Product expires 6 months after freezing if stored at -20°C.

**Placebo capsules:** Placebo capsules will be identical in appearance to DE capsules but will not have human feces, the active pharmaceutical ingredient. The placebo capsules are filled with Sodium Chloride (0.9%, USP), Glycerol (12.5%, USP) and deionized water to the previously stated volume specification. Capsules are stored frozen at -80°C before dispensing to local site storage. Placebo will be administered the same as the daily arm of the trial.

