## **9.6. Randomization and Blinding of Study Drug**

Participants meeting the eligibility criteria and willing to consent to the study procedures will be randomized on a 1:1:1 basis with block sizes of 10 to receive one of the following treatments:

1. Daily FMT treatment with 5 capsules/day
2. One-time FMT treatment of 30 capsules
3. Daily placebo (5 capsules/day)

Randomization will be carried out by the UW PRC so that the research team and treatment team remains blinded to whether the patient is receiving FMT or placebo.

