After the baseline clinical assessment and stool sample have been collected, subjects in groups 1 and 3 (daily FMT and daily placebo) are eligible to undergo administration of the intervention (DE or placebo) in

accordance with the randomization schedule. The intervention will be administered by the blinded treatment staff and the participant observed for 30 minutes following administration. Post-ingestion observation of inpatients will only occur after the first dosing; subsequent inpatient dosing will be administered by a study physician/nurse but do not require 30 minutes of observation. Pre-intervention vital signs (as previously described) will be collected or abstracted from the medical record prior to first dose. Participants will be provided with information regarding monitoring for minor and severe adverse event related to the intervention administration. Participants will be encouraged to report any concerning symptoms to staff. Oral nutrition may commence 1 hour post-capsules administration. Study staff do not need to collect a blood sample to check for neutropenia prior to dosing.

For all patients, a baseline stool sample will be collected and all patients should begin to fill out their patient diary starting on Day 0. If a patient is unable to provide a stool sample, peri-rectal swabs may be collected.

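### Blocks of 10 cannot give 1:1:1 over three arms, and the single-dose arm cannot be double-blind because no 30-capsule placebo exists

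*Combined protocol and SAP*

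**What the plan says.** On allocation, Section 7.1 states: "Patients will be randomized at a 1:1:1 ratio using permuted blocks (block size=10). Randomization will be double-blinded". Section 9.6 repeats that patients are "randomized on a 1:1:1 basis with block sizes of 10 to receive one of the following treatments" and lists daily FMT, one-time FMT and daily placebo. Section 2 plans 30 patients, 10 per arm.

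On blinding, the title in Section 2 calls this a "randomized, double-blind placebo-controlled trial". Section 9.6 has the pharmacy randomise so that the "research team and treatment team remains blinded to whether the patient is receiving FMT or placebo". Section 11.2 describes the person who delivers the 30 capsules to Group 2 as blinded.

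On the regimens:
- Placebo (Section 2): "5 capsules of oral placebo per day undergoing antibiotic treatment and for 7 days following conclusion of antibiotic treatment". Section 9.1 adds: "Placebo will be administered the same as the daily arm of the trial".
- Group 2 (Section 7.1): "This group will receive 30 oral FMT capsules one time 48-72 hours following completion of antibiotic treatment".
- First dosing (Section 11.1, Baseline): "subjects in groups 1 and 3 (daily FMT and daily placebo) are eligible to undergo administration of the intervention". Group 2 is not dosed then.

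**The concern.** The block size and the allocation ratio cannot both be honoured, so the pharmacy has to invent a rule before it can draw up the list. Whether the arms end at 10:10:10 depends on that unwritten rule.

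The blinding claim is unqualified, but the single-dose regimen has no placebo counterpart. The secondary objective in Section 6 compares both FMT regimens with placebo on safety and feasibility. Adverse event reporting, the symptom component of CDI and retention (Sections 7.2.2 and 7.2.3) all depend on what patients report or choose and on what staff record. Each can shift when both know that FMT was assigned. If the text stays, the report would describe the comparison of Group 2 with placebo as double-blind when one side of it is not.

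**Working it through.** **Planned total.** Section 2 gives N = 30 and three arms: 30 / 3 = 10 per arm. The plan's figure reproduces.

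**Block rule.** 10 = 3 × 3 + 1, so a block of 10 leaves one slot over, and the nearest split is 4:3:3. Thirty patients fill 30 / 10 = 3 blocks. Each arm then has 3 × 3 = 9 slots plus whatever extra slots it receives, with three extra slots in all:

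- Extra slot rotated over the arms: one each, 10:10:10 with certainty.
- Extra slot always in the same arm: 12:9:9.
- Extra slot placed independently and with equal chance in each block (an assumption, since no rule is given): 3³ = 27 equally likely placements. One per arm: 3! = 6, so 6/27 = 22.2% for 10:10:10. Two in one arm and one in another: 3 × 2 × 3 = 18, so 18/27 = 66.7% for 11:10:9. All in one arm: 3/27 = 11.1% for 12:9:9.

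**Regimens side by side** (Sections 2, 7.1, 9.1, 9.6 and 11.1):

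| Arm | During antibiotics | After antibiotics | Matching placebo |
|---|---|---|---|
| Group 1, daily FMT | 5 capsules a day | 5 a day for 7 days | Group 3 |
| Group 2, single-dose FMT | none | 30 capsules once, at 48-72 hours | none |
| Group 3, placebo | 5 capsules a day | 5 a day for 7 days | – |

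A patient with no daily capsules can only be in Group 2, and Group 2 receives only FMT. Assignment is visible from baseline, before the 30 capsules are given. Other procedures also differ: pre-dose fasting is 8 hours for Group 2 and 2 hours for the daily arms (Sections 5.5 and 7.1), only the daily arms keep a dosing diary (Section 9.7), and the calendar in Section 17.2 codes the two kinds of arm separately.

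**Extent.** 10 of 30 patients (33%); 10 of the 20 assigned to FMT (50%); one side of one of the two comparisons of FMT with placebo.

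**Why a small block is not the remedy.** Group 2 allocations are visible, so anyone who knows the block size can sometimes tell whether the next patient will be in Group 2. For a block with g Group 2 slots and h others, the expected number of slots known with certainty in advance is h/(g+1) + g/(h+1):

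- Blocks of 3: (2/2 + 1/3) / 3 = 44.4% of slots.
- Blocks of 6: (4/3 + 2/5) / 6 = 28.9%.
- One list of 30: (20/11 + 10/21) / 30 = 7.6%.
- Blocks of 10 with a rotated extra slot, order of rotation not known beforehand: 13.0%, by enumerating the same events.

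The protocol prints the block size in two sections, so knowledge of it at the site is plausible.

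**The case against.** The strongest reply is that little depends on this. The primary outcome comes from sequencing, and samples carry only an ID number (Section 10). CDI needs PCR as well as symptoms (Section 7.2.2). Relatedness enters none of the outcomes in Section 7.2.3. An effect on the halting rule in Section 13.5.1 is possible but not shown, because the definition of a related event in Section 13.2.2 asks for recurrence on re-exposure, which a one-time dose can hardly supply. The trial is a pilot whose size was set by availability (Section 12.1). All of this stands and limits the weight of the point. It does not make either statement correct.

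A second reply is that Section 9.4 speaks of FMT or placebo as 5 capsules daily or 30 once. Read alone, that could suggest a 30-capsule placebo. The arm definitions in Sections 2, 7.1, 9.1 and 9.6 contain none, so the sentence needs reconciling and does not supply a matched control.

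Three stronger readings are tempting but not supported:

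- A reader might infer that the planned 10 per arm is wrong. It is not: 10:10:10 is reachable, but the rule that would guarantee it is missing.
- A reader might infer from Section 8.4.2.2 that the two daily arms will also be unmasked. For antibiotics beyond 14 days it assigns the 30-capsule FMT dose to Group 1 and stops daily capsules in Groups 2 and 3. Taken literally, that would separate daily FMT from placebo. But Group 2 has no daily capsules to stop, so the passage conflicts with the group definitions in Section 7.1 and cannot be taken at face value. Sections 8.4.1 and 8.4.2.2 also target short courses, and the share of longer ones is not given. No number of affected patients can be derived.
- A reader might infer that the arm-specific brochure in Section 8.4.2.2 reveals FMT or placebo. It covers post-discharge procedures, and Section 11.2 sets those out jointly for Groups 1 and 3.

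**Conclusion.** Both statements are wrong as written and should be corrected. No block of 10 can be 1:1:1 over three arms, and the final 10:10:10 is not guaranteed by the text. Its probability is 22% if the extra slot is placed at random, which is an assumption; it is certain under rotation and impossible under a fixed template. The double-blind claim fails for Group 2, 10 of 30 patients; this follows from the arm definitions and needs no assumption. Daily FMT against daily placebo can still be double-blind.

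It would go too far to conclude that the trial's results are seriously biased. The exposed outcomes are secondary or safety measures, the sequencing and PCR outcomes are little exposed, and the documents offer no basis for a large effect. The fault is a design description that does not match the design.

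**What to change.** 1. In Sections 7.1 and 9.6, replace the block rule with one that can deliver 1:1:1 overall and 10:10:10: either one permuted list of 30, or blocks of 10 with the extra slot rotated over the arms. Avoid small blocks, for the reason shown in the working. Keep the block details in a document held by the pharmacy and out of the protocol text. A single list is less predictable; rotated blocks keep the arms closer to balance if enrolment stops short. If enrolment has begun, which the documents do not say, document the list actually used.
2. In the title and Sections 2, 7.1, 9.6 and 11.2, limit the claim, for example: *allocation to daily FMT or daily placebo is double-blind; allocation to single-dose FMT is known to patient and staff*. Reconcile Section 9.4 with the arm definitions.
3. Report Group 2 against placebo on adverse events, symptom-based CDI and retention as not blinded, and tell the data monitoring committee so.
4. Separately, reconcile the group numbering in Section 8.4.2.2 with Section 7.1. No view is taken on which is right.

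The cost is a few lines of text and, if enrolment has not begun, a new list. The downside is a more modest blinding claim, and relabelling does not remove whatever bias the open arm carries.

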Study staff must inform participants that the trial involves research, and explain the purpose of the trial, those aspects of the trial that are experimental, any expected benefits, all possible risks, the expected duration of the participant's participation in the trial, the procedures of the research study, and the probability for random assignment to treatment groups. Participants will be informed they will be notified in a timely manner if information becomes available that may be relevant to their willingness to continue participation in the trial. They must also be informed of alternative procedures that may be available, and the important potential benefits and risks of these available alternative procedures. Participants and/or legal guardian must receive an explanation as to whether any compensation and any medical treatments are available if injury occurs, and, if so, what they consist of, or where further information may be obtained. Participants and/or substitute decision maker/proxy guardian must be informed of the anticipated financial expenses, if any, to the participant for participating in the trial, as well as any anticipated prorated payments, if any, to the participant for participating in the trial. They must be informed of whom to contact (e.g., the PI or study physician/nurse practitioner) for answers to any questions relating to the research project. Information will also include the foreseeable circumstances and/or reasons under which the participant's participation in the trial may be terminated. The participants and/or substitute decision maker/proxy must be informed that participation is voluntary and that they are free to withdraw from the study for any reason at any time without penalty or loss of benefits to which the participant is otherwise entitled.

Neither the investigators, nor the trial staff, will coerce or unduly influence a participant to participate or continue to participate in the trial. The extent of the confidentiality of the participants' records must be defined, and participants must be informed that applicable data protection legislation will be followed. Participants and/or substitute decision maker/proxy must be informed that the monitor(s), auditors(s), IRB and regulatory authority(ies) will be granted direct access to the participant's medical records for

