### *Group 2 (single dose FMT): Visit will occur in a clinical setting*

Capsules will be delivered to the patient by a blinded member of the treatment team 48-72 hours following antibiotic treatment completion. If the patient is discharged he/she will be asked to return to the clinic 48-72 hours following completion of his/her antibiotics to consume the 30 capsules under supervision of a nurse or physician. Study staff do not need to collect a blood sample to monitor for neutropenia. During this visit the following will occur:

- Vitals collection
- Physical exam
- Clinical symptoms assessment
- Diet assessment
- Concomitant medications
- Stool sample
- FMT dosing
- Adverse events assessment
- 30 minute post-dose observation

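### The trial is labelled double-blind without exception, but the single-dose arm has no matching placebo, so only daily FMT versus daily placebo can be masked

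*Combined protocol and SAP*

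**What the plan says.** The blinding claims carry no exception for any arm. The title in Section 2 describes a "randomized, double-blind placebo-controlled trial", and Section 7.1 states: "Randomization will be double-blinded". Section 9.6 makes the claim for staff, with randomization handled by the Pharmaceutical Research Center "so that the research team and treatment team remains blinded to whether the patient is receiving FMT or placebo". Section 11.2 applies it to the single-dose arm (Group 2): "Capsules will be delivered to the patient by a blinded member of the treatment team 48-72 hours following antibiotic treatment completion".

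The regimens are these. Section 2 gives the reference therapy as "Placebo: 5 capsules of oral placebo per day undergoing antibiotic treatment and for 7 days following conclusion of antibiotic treatment". Section 9.1 adds: "Placebo will be administered the same as the daily arm of the trial". Sections 7.1 and 9.6 list three arms: daily FMT (5 capsules), one-time FMT (30 capsules) and daily placebo (5 capsules). Neither a 30-capsule placebo nor dummy daily capsules for Group 2 appears anywhere.

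On Day 0, Section 11.1 says that "subjects in groups 1 and 3 (daily FMT and daily placebo) are eligible to undergo administration of the intervention". Group 2 takes nothing until 48-72 h after the antibiotics end. Under Section 8.5.1, consent must cover "the procedures of the research study, and the probability for random assignment to treatment groups".

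**The concern.** A placebo masks an arm only if it is given on that arm's schedule. Here the placebo matches the daily FMT schedule and nothing else, so seeing the one-time schedule is the same as seeing FMT. The plan nevertheless says that staff cannot tell FMT from placebo in any arm, and describes the person who hands over the 30 capsules as blinded.

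One of the two FMT-placebo comparisons is affected. Section 6 makes the safety and feasibility of both FMT regimens against placebo a secondary objective, and Section 7.2.3 makes adverse-event proportions the primary safety measures. If the single-dose results on these measures are reported as double-blind, readers will credit them with a protection against expectation effects that the design does not provide.

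**Working it through.** **Inputs.** 30 participants, 1:1:1, 10 per arm (Sections 2, 9.6, 12.1); regimens by arm (Sections 2, 7.1, 9.1, 9.6). The planned total reproduces: 3 × 10 = 30. The sample size has no power basis (Section 12.1), so there is no power figure to check.

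**Step 1: what the schedule reveals.**
- P(FMT | one-time regimen) = 10/10 = 100%.
- P(FMT | daily regimen) = 10/(10 + 10) = 50%.
- Before any schedule is seen, P(FMT) = 20/30 = 67%.

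**Step 2: how many are identifiable as FMT.**
- Whole trial: 10/30 = 33%.
- Single-dose versus placebo: 10/20 = 50%. The other 10, on placebo, are not identifiable as placebo, because they share their schedule with daily FMT.

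**Step 3: when it shows.** Section 11.1 allows first dosing on Day 0 for Groups 1 and 3 only, while the schematic in Section 3 puts randomization on Day 1. Some daily participants may start a little later, since Section 5.5 has outpatients return for the first dose. The regimen is therefore visible from about Day 0 to 1.

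**Step 4: who can see it.**
- Staff who give the Group 2 dose (Section 11.2).
- Staff who make the weekly calls: only daily participants get capsule reminders and pill counts (Sections 8.4.2.2, 11.2), and the same calls record adverse events (Section 11.2).
- Participants, if they have been told the regimens. Section 8.5.1 implies that they will be, but the consent form is a separate document (Section 8.5.2) that was not available.

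**Step 5: which outcomes depend on it.**
- Exposed: adverse-event proportions counted from randomization (Section 7.2.3), relatedness (Section 13.2.2), patient diaries (Sections 7.1, 11.2), and the symptom component of CDI, which also needs toxin PCR (Section 7.2.2).
- Much less exposed: the sequencing primary outcome (Section 7.2.1), because samples carry only coded identifiers (Sections 10, 12.4). That laboratory staff are masked to arm is not stated.

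**Step 6: resolution.** All randomized subjects enter the safety analysis (Section 8.6.2.1), so the denominator is 10 per arm, and one participant whose reporting changes moves a proportion by 1/10 = 10 points. This shows how coarse the comparison is; it is not an estimate of bias.

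**Step 7: whether the daily comparison stays masked.** Capsules and packaging are identical (Sections 9.1, 9.2), which supports it. Section 8.4.2.2 does not. For antibiotic courses beyond 14 days it gives Group 1 a 30-capsule dose and ends daily treatment in Groups 2 and 3, whereas Sections 7.1 and 9.6 define Group 1 as daily FMT and Group 2 as one-time FMT. Applied as written, this would handle Groups 1 and 3 differently and so separate them.

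**The case against.** The strongest reply is that little hangs on the label. The primary outcome is sequencing on coded samples, CDI needs PCR as well as symptoms, Section 2 plans only descriptive safety summaries, and this is a pilot with no powered test. That stands as a limit on consequence. It does not remove the point: Section 6 sets FMT against placebo on safety for both regimens, and Section 12.3 provides for tests between intervention and control groups at a two-sided 0.05.

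A second reply is textual. Section 9.4 mentions FMT or placebo together with a one-time 30-capsule dose, and Section 6 speaks of placebo groups in the plural. Neither creates an arm. Section 9.4 ties the dose to the treatment group, and no listed group has a 30-capsule placebo.

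Some stronger readings are tempting but not supported:
- **The whole trial is unmasked.** The daily arms share schedule, capsules and packaging, so they can be masked from each other once Section 8.4.2.2 is reconciled.
- **Every single-dose participant certainly knows from the baseline visit.** Section 9.6 speaks only of staff, the participants' knowledge depends on a consent form not seen, and the timing is Day 0 or Day 1.
- **The single-dose safety results, or the halting rules in Section 13.5.1, will be biased by a known amount or in a known direction.** The documents give no event or relatedness rates. Section 13.2.2 also asks that a related event recur on re-exposure, which a single dose cannot show.

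**Conclusion.** The plan states a property that the design does not have. The single-dose arm, 10 of 30 participants and half of the single-dose versus placebo contrast, is identifiable as FMT to staff who know the arms from about Day 0 to 1, and to participants if consent describes the regimens. Only daily FMT versus daily placebo can be masked.

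The counts assume the planned 10 per arm. The staff part follows from the regimens and needs only that staff know the arms; the participant part is conditional on the consent form. The effect is confined mainly to single-dose versus placebo results that depend on reporting or judgement, and its size cannot be derived. A reader might infer that the microbiome findings are compromised as well; the coded sample labels argue against that, although masking of the laboratory should be stated. This should be corrected before the single-dose contrasts are reported.

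**What to change.** 1. In the title and Sections 2, 7.1 and 9.6, limit the double-blind description to daily FMT versus daily placebo. In Section 11.2, correct the statement that the person delivering the Group 2 capsules is blinded.
2. State that single-dose contrasts on CDI, diaries and adverse events will be reported as not blinded.
3. State that staff who process and sequence samples work without arm information.

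Separately, the group labels in Section 8.4.2.2 for antibiotic courses over 14 days conflict with the arm definitions in Sections 7.1 and 9.6. These passages must be reconciled before the daily comparison is called double-blind.

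The cost is text changes in a few sections; the arms and sample size do not change. Item 3 may need tasks split if the laboratory staff who receive returned capsules (Sections 9.7, 11.2) also handle samples. The downside is a weaker but accurate label for the single-dose comparison, and the expectation bias itself remains.
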